4.2. Exclusion Criteria

1. Have a history of another primary malignancy within 3 years except: a. adequately treated *in situ* carcinoma of the cervix, non-melanoma carcinoma of the skin, b. any other untreated cancer deemed by treating physician to be at low risk for progression during the study period (such as low or intermediate risk prostate cancer), c. curatively treated malignancy that is not expected to have recurrence or require treatment during the course of the study.
2. Have uncontrolled bladder cancer. Patients with bladder cancer must have bladder cleared of disease by transurethral resection prior to initiating treatment and must not be at need for systemic therapy.
3. Have any other medical condition that would, in the investigator's judgment, prevent the subject's participation in the clinical study due to safety concerns or compliance with clinical study procedures.
4. Have current evidence of corneal or retinal disorder/keratopathy including, but not limited to, bullous/band keratopathy, corneal abrasion, inflammation/ulceration, keratoconjunctivitis, confirmed by ophthalmologic examination. Subjects with asymptomatic ophthalmologic conditions assessed by the investigator to pose minimal risk for study participation may be enrolled in the study.
5. Have a history and/or current evidence of extensive tissue calcification including, but not limited to, the soft tissue, kidneys, intestine, myocardium, vasculature and lung with the exception of calcified lymph nodes, minor pulmonary parenchymal calcifications, and asymptomatic coronary calcification.
6. Have impairment of gastrointestinal (GI) function or GI disease that may significantly alter the absorption of oral infigratinib (e.g., ulcerative diseases, uncontrolled nausea, vomiting, diarrhea, malabsorption syndrome, small bowel resection).
7. Have current evidence of endocrine alterations of calcium/phosphate homeostasis, e.g., parathyroid disorders, history of parathyroidectomy, tumor lysis, tumoral calcinosis etc.
8. Are currently receiving treatment with agents that are known strong inducers or inhibitors of CYP3A4 and medications which increase serum phosphorus and/or calcium concentration. Subjects are not permitted to receive enzyme-inducing anti-epileptic drugs, including carbamazepine, phenytoin, phenobarbital, and primidone.
9. Have consumed grapefruit, grapefruit juice, grapefruit hybrids, pomegranates, star fruits, pomelos, Seville oranges or products containing juice of these fruits within 7 days prior to first dose of study drug.
10. Have used medications known to prolong the QT interval and/or are associated with a risk of Torsades de Pointes (TdP) 7 days prior to first dose of study drug.
11. Have used amiodarone within 90 days prior to first dose of study drug.

12. Are currently using therapeutic doses of warfarin sodium or any other coumadin - derivative anticoagulants or using direct thrombin inhibitors (e.g., argatroban) or Factor Xa inhibitors (e.g., rivaroxaban) that are primarily metabolized by CYP3A4. Heparin and/or low molecular weight heparins or direct thrombin inhibitors and/or Factor Xa inhibitors that are not metabolized by CYP3A4 (e.g., dabigatran, edoxaban) are allowed.
13. Have insufficient bone marrow function:
 - a. Absolute neutrophil count (ANC) $< 1,000/\text{mm}^3 (1.0 \times 10^9/\text{L})$
 - b. Platelets $< 100,000/\text{mm}^3 (75 \times 10^9/\text{L})$
 - c. Hemoglobin $< 9.0 \text{ g/dL}$
14. Have insufficient hepatic and renal function:
 - a. Total bilirubin $> 1.5 \times$ upper limit of normal (ULN) (unless documented Gilbert's syndrome)
 - b. AST/ serum glutamic-oxaloacetic transaminase (SGOT) and ALT/ serum glutamic-pyruvic transaminase (SGPT) $> 2.5 \times$ ULN (AST and ALT $> 5 \times$ ULN in the presence of liver involvement of cholangiocarcinoma)
 - c. Calculated or measured creatinine clearance of $< 30 \text{ mL/min}$
15. Have amylase or lipase $> 2.0 \times$ ULN
16. Have abnormal calcium-phosphate homeostasis:
 - a. Inorganic phosphorus $>$ ULN
 - b. Total corrected serum calcium $>$ ULN
17. Have clinically significant cardiac disease including any of the following:
 - a. Congestive heart failure requiring treatment (New York Heart Association Grade ≥ 2), LVEF $< 50\%$ or local lower limit of normal as determined by echocardiogram (ECHO), or uncontrolled hypertension (refer to the European Society of Cardiology and European Society of Hypertension guidelines [[Williams et al., 2018](#)])
 - b. Presence of Common Terminology Criteria for Adverse Events (CTCAE) v5.0 or later Grade ≥ 2 ventricular arrhythmias, atrial fibrillation, bradycardia, or conduction abnormality
 - c. Unstable angina pectoris or acute myocardial infarction ≤ 3 months prior to first dose of study drug
 - d. QTcF $> 470 \text{ msec}$ (males and females). Note: If the QTcF is $> 470 \text{ msec}$ in the first ECG, a total of 3 ECGs separated by at least 5 minutes should be performed. If the average of these 3 consecutive results for QTcF is $\le 470 \text{ msec}$, the subject meets eligibility in this regard
 - e. Known history of congenital long QT syndrome
18. Have had a recent (≤ 3 months) transient ischemic attack or stroke

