Gra de 3 (ANC < $1.0 - 0.5 \times 10^9/L$)	
Hold dose of infigratinib until resolved to CTCAE Grade \leq 1 or baseline, then
 
 • If resolved within \leq 7 days, maintain dose level of infigratinib • If resolved between > 7 days and 14 days, \downarrow 1 dose level of infigratinib • If not resolved within \leq 14 days, discontinue subject from study drug
Gra de 4 (ANC < $0.5 \times 10^9/L$)	
Hold dose of infigratinib until resolved to CTCAE \leq Gra de 1, \downarrow 1 dose level of infigra tinib
 
 • If not resolved within \leq 14 days, discontinue subject from study drug
Febrile Neutropenia	
Gra de 3 (ANC < $1.0 \times 10^9/L$, single temperature of > $38.3^{\circ}C$ or a sustained temperature of $\geq 38.0^{\circ}C$)	
Hold dose of infigratinib until resolved to CTCAE Grade \leq 1, then
 
 • If resolved within \leq 7 days, \downarrow 1 dose level of infigratinib. • If not resolved within 7 days, discontinue subject from study drug
Gra de 4	Discontinue subject from study drug
Anemia	
Gra de 3 (hemoglobin < 8.0 g/dL)	Hold dose of infigratinib until resolved or corrected to CTCAE Grade \leq 1 or baseline, then maintain dose level
Gra de 4	Hold dose of infigratinib until resolved or corrected to CTCAE Grade \leq 1 or baseline, then \downarrow 1 dose level
Platelet Count Decreased (Thrombocytopenia)	
Grade 3 (platelet < $50 - 25 \times 10^9/L$) without \geq Gra de 2 bleeding	
Hold dose of infigratinib until resolved to CTCAE Grade \leq 1 or baseline
 
 • If resolved within \leq 7 days, maintain dose level of infigratinib • If resolved between > 7 days and 14 days, \downarrow 1 dose level of infigratinib • If not resolved within \leq 14 days, discontinue subject from study drug
Grade 3 (platelet < $50 - 25 \times 10^9/L$) with bleeding or Grade 4 (platelet < $25 \times 10^9/L$)	
Hold dose of infigratinib until resolved to CTCAE Grade \leq 1 or baseline, then \downarrow 1 dose level
 
 • If not resolved within \leq 14 days, discontinue subject from study drug

Worst Toxicity CTCAE (v5.0) Grade (Unless Otherwise Specified)	Recommended Dose Modifications any Time During a Cycle of Therapy
INVESTIGATIONS – RENAL	
Serum Creatinine	

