8.2.7. Ophthalmic Assessments

Ophthalmologic examination will be performed by an ophthalmologist, or optometrist who is supervised by an ophthalmologist, at the times indicated in [Section 1](#). These assessments will include visual acuity testing, slit lamp examination of the anterior eye segment, intraocular pressure, and fundoscopy. Additional examinations such as specular microscopy (that enables a magnified, direct view of the corneal epithelium), corneal pachymetry, retinal optical coherence tomography (OCT), and dilated fundoscopy will be performed as clinically indicated.

9. STATISTICAL PLAN:

The primary objective is to evaluate the safety and tolerability of infigratinib as neoadjuvant therapy. Up to 20 patients will be enrolled in the study. The study will estimate proportion of patients who are not able to complete treatment (discontinuation) due to excessive toxicity along with the 90% exact confidence interval (NOTE: excessive toxicity is defined as treatment related adverse events that cause patients not to complete 2-cycles of planned treatment schedule). Toxicities will be tabulated using frequency and percentage by grade and their relations to treatment. Assuming a 30% of discontinuation due to excessive toxicity, the 90% confidence interval would be (13.1%, 46.9%) with a sample size of 20. Toxicity data will be summarized for the whole group of patients and for patients with eGFR \geq 50 and eGFR 30-49 separately. The safety analysis included all patients who received at least one dose of infigratinib.

Toxicity monitoring:

The study will monitor the incidence of not completing treatment or delay >14 days of surgery due to excessive toxicity using this monitoring rule. That is stop the trial early if $\text{Prob}(\text{Ptox} > 0.3 | \text{data}) > 0.85$. Where Ptox denotes the proportion of patients not being able to complete treatment or delay >14 days of surgery. The corresponding stopping boundaries are that the trial will be stopped early if at any time it is observed that $(n \text{ of patients not completing treatment or delay } >14 \text{ days of surgery due to excessive toxicity} / N \text{ of patients treated}) \geq 3/5, 4/(6-8), 5/(9-10), 6/(11-13), 7/(14-16), \text{ and } 8/(17-19)$. This stopping rule will be applied for each cohort of eGFR \geq 50 and eGFR 30-49 separately. If one cohort stops early due to excessive toxicity, the other will continue accruing as per protocol criteria and toxicity monitoring rule.

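### Exclusion 13b prints two platelet cut-offs that disagree: 100,000/mm³ is 100×10⁹/L, but the parenthesis says 75×10⁹/L

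*Combined protocol and SAP*

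**What the plan says.** Section 4.2, item 13 ("Have insufficient bone marrow function"), lists three laboratory limits. Two of them are given in both conventional and SI units:

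- 13a, neutrophils: "Absolute neutrophil count (ANC) $< 1,000/\text{mm}^3 (1.0 \times 10^9/\text{L".
- 13b, platelets: "Platelets $< 100,000/\text{mm}^3 (75 \times 10^9/\text{L".

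The third, 13c for hemoglobin, is given in one unit only.

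The only other platelet levels in the document are in Section 5.2.5.1, Table 2, under "Platelet Count Decreased (Thrombocytopenia". They apply to patients already on treatment and appear only in 10⁹/L. The first hold level is a count below 50×10⁹/L; the more severe row reads "Grade 3 (platelet < $50 - 25 \times 10^9/L$) with bleeding or Grade 4 (platelet < $25 \times 10^9/L".

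Section 9 (Statistical Plan) caps the trial: "Up to 20 patients will be enrolled in the study". It defines the safety set by dosing: "The safety analysis included all patients who received at least one dose of infigratinib".

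**The concern.** An eligibility limit has to give one answer for each candidate. As printed, 13b gives two. A screener who applies the leading figure excludes a candidate at, say, 80×10⁹/L; one who applies the figure in parentheses does not. If such a patient were enrolled, a monitor could not tell from the text alone whether a deviation had occurred.

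The criterion reaches everyone screened. Hematology is drawn at screening (Section 7.2), and the hematology panel includes platelets (Section 8.2.3, Table 6). Because Table 2 uses 10⁹/L alone, someone working in that unit could plausibly read 75 from 13b, though the document does not state which unit the screening laboratory reports.

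What is at stake is consistent screening and a clear record of who was eligible, in patients who go on to nephroureterectomy, ureterectomy or ureteroscopic management. The statistical design is not at stake.

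**Working it through.** **Inputs**

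- Platelet limit, leading figure: 100,000/mm³ (Section 4.2, 13b).
- Platelet limit, parenthesis: 75×10⁹/L (Section 4.2, 13b).
- Neutrophil limit: 1,000/mm³, parenthesis 1.0×10⁹/L (Section 4.2, 13a).
- First on-treatment platelet hold level: below 50×10⁹/L (Section 5.2.5.1, Table 2).
- Maximum enrolment: 20 (Section 9).

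**Formula**

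1 L = 10⁶ mm³, so a count in units of 10⁹/L = (count per mm³) × 10⁶ ÷ 10⁹.

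**Step 1: test the notation on 13a.** 1,000 × 10⁶ ÷ 10⁹ = 1.0×10⁹/L. This reproduces the printed figure exactly, so the parenthesis in this list is the SI equivalent of the leading figure.

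**Step 2: apply the same conversion to 13b.** 100,000 × 10⁶ ÷ 10⁹ = 100×10⁹/L. The document prints 75×10⁹/L, so its figure is not reproduced.

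**Step 3: convert the other way.** 75×10⁹/L ÷ 10⁶ mm³/L = 75,000/mm³, not 100,000/mm³.

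**Step 4: size of the disagreement.** 100 − 75 = 25×10⁹/L, which is 25/100 = 25% of the leading figure. The disputed band is 75 to just under 100×10⁹/L:

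| Platelets (10⁹/L) | Leading figure (<100) | Parenthesis (<75) |
|---|---|---|
| Below 75 | excluded | excluded |
| 75 to just under 100 | excluded | not excluded |
| 100 and above | not excluded | not excluded |

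**Step 5: position against the treatment rules.** The lowest admissible count lies 100 − 50 = 50×10⁹/L above the first hold level on one reading and 75 − 50 = 25×10⁹/L above it on the other. Neither reading admits a patient who would already meet a platelet hold on day 1.

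**Step 6: does any other text settle it?** Section 4.1 gives no platelet limit. Table 2 gives only on-treatment levels, which are compatible with either figure. Exclusion 3 allows investigator judgment but sets no number. The document therefore does not show which figure was intended.

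**Step 7: effect on the statistics.** The confidence interval and stopping boundaries in Section 9 depend on the number treated and the number with the toxicity outcome, and the safety set depends on receiving a dose. None of them uses a platelet threshold. For scale only, one enrolled patient in the disputed band would be 1/20 = 5% of maximum enrolment.

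**The case against.** The best reply concerns weight, since the arithmetic is not open to dispute. The less-than sign is attached to 100,000/mm³, and the parenthesis has no operator of its own. On a literal reading the leading figure is the rule and the parenthesis is a faulty gloss, so a candidate at 80×10⁹/L is excluded as written. Inconsistent screening would require someone to prefer the gloss to the rule, and nothing in the document shows that happening. Both figures lie above the first hold level, platelets are rechecked during treatment and before surgery (Sections 1, 7.5 and 8.2.3), and an investigator can exclude on safety grounds under exclusion 3. On this view it is a clerical slip, and the sponsor should be asked which figure was meant before a correction is proposed.

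Much of this stands. No harm is shown, no analysis changes, and most sites would probably use the leading figure. It does not make the criterion correct, though. Two contradictory numbers stand in an operative eligibility rule, and which one governs has to be inferred. Investigator judgment does not answer that question.

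A reading error from the PDF is also conceivable, since the source file was not available. It is unlikely: both numbers are intact, and the adjacent line converts correctly.

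On the order of the remedy, defaulting to 100×10⁹/L is a cautious choice and not something the document proves. That is why the alternative correction is kept open for the sponsor.

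**Conclusion.** The criterion is wrong as written. The two cut-offs in 13b differ by 25×10⁹/L (25% of the leading figure), and candidates from 75 to just under 100×10⁹/L are classified differently by each. The conclusion rests on the unit conversion, on reading the parenthesis as a restatement (as 13a supports), and on the extracted text being faithful to the source.

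The consequences are limited. How many candidates fall in the band is unknown and may be none. The error should be corrected because it sits in a rule applied to every candidate, not because any result is shown to be at risk.

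One nearby feature fits an incomplete edit without proving it: exclusion 14b still refers to liver involvement of cholangiocarcinoma in a trial of upper tract urothelial carcinoma.

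**What to change.** Change 13b so that both units state the same limit:

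- **Default:** Platelets <100,000/mm³ (100×10⁹/L). This keeps the leading figure, to which the comparison sign is attached, and it is the more conservative of the two.
- **If the sponsor confirms that 75 was intended:** Platelets <75,000/mm³ (75×10⁹/L).

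The cost is a one-line protocol correction, with no change to the design, sample size, monitoring rule or analysis.

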5. TREATMENTS

5.1. Treatments Administered

Patients will receive infigratinib 125 mg orally every day for a total of 2 cycles. Each cycle will consist in 28 days, with a schedule of 3 weeks on, 1 week off. Surgery will be performed during weeks 8-9 (week 8 being the off-week of 2nd cycle), and patients will have taken last dose of Infigratinib at least 48 hours prior to surgery.

If patients are not able to tolerate the study drug, every effort will be made to schedule the surgery as soon as possible after the patient has recovered and/or the investigator determines it is the best course of action for the patient.

5.2. Information on Infigratinib

5.2.1. Subject Instructions for Infigratinib Dosing

Subjects should be instructed to take the daily dose of infigratinib in the morning, at approximately the same time each day (24 ± 2 hour interval).

Infigratinib should be taken in the fasted state at least 1 hour before or 2 hours after a meal. It should be taken with a large glass of water (~250 mL) and consumed over as short a time as possible. Subjects should be instructed to swallow the capsules whole and not chew them.

If the subject forgets to take the scheduled dose of infigratinib in the morning, he/she should not take the dose more than 2 hours after the usual time and should continue treatment the next day. Any doses that are missed should be skipped altogether and should not be replaced or made up at the next scheduled dosing.

If vomiting occurs following dosing with infigratinib, re-dosing is not permitted the same day. Dosing should resume the next day.

Infigratinib is characterized by pH-dependent solubility; therefore, medicinal products that alter the pH of the upper GI tract may alter the solubility of infigratinib and limit bioavailability. These agents include, but are not limited to, proton pump inhibitors (e.g., omeprazole), H₂-antagonists (e.g., ranitidine) and antacids. If possible, proton pump inhibitors should be avoided due to their long pharmacodynamic effect and replaced with H₂-antagonists or antacids. Infigratinib should be taken at least 2 hours before or 10 hours after dosing with a gastric protection agent.

Subjects must avoid the consumption of grapefruits, grapefruit juice, grapefruit hybrids, pomegranates, star fruits, pomelos, Seville oranges or juice within 7 days prior to the first dose of infigratinib and throughout the treatment period. This is due to a potential CYP3A4 interaction with study drug. Normal oranges and orange juice are allowed.

Last dose of Infigratinib should be at least 48 hours prior to surgery.

5.2.2. Description and Dispensing of Infigratinib

Infigratinib will be supplied as hard gelatin capsules for oral use at dose strengths of 25 and 100 mg. Excipients will include microcrystalline cellulose, lactose monohydrate, HPMC2910, crospovidone, colloidal silicon dioxide, magnesium stearate, and hard gelatin

capsule. Infigratinib will be manufactured under Good Manufacturing Practice for investigational use.

5.2.3. Packaging and Labeling

Infigratinib capsules will be packaged in high density polyethylene bottles with child resistant closures. Study drug labels will be in the local language and comply with the legal requirements of each country. Labels will include storage conditions for the drug.

5.2.4. Study Drug Accountability, Handling, and Disposal

Infigratinib capsules will be received by designated personnel at the study site, handled and stored safely and properly, and kept in a secured location to which only the investigator and designated site personnel have access. Upon receipt, infigratinib should be stored according to the instructions specified on the drug label and in the Investigator's Brochure . Refer to the Pharmacy Manual for further details.

The investigator or designee must maintain an accurate record of the shipment and dispensing of infigratinib in a drug accountability log. Subjects will be asked to return all used and unused bottles of infigratinib and packaging on a regular basis, at the end of the study, or at the time of study drug discontinuation. Drug accountability will be assessed by the investigator's delegated study personnel, and captured in a subject drug accountability log. This information must be captured in the source document at each subject visit.

At study close-out, infigratinib will be destroyed per UTMDACC Institutional Policy # ADM0166.

5.2.5. Dose Modifications for Infigratinib

Each subject will be allowed a maximum of 2 dose reductions as noted in Table 2. Subjects should discontinue infigratinib if toxicity persists as per criteria in Table 3. Subject management will be based upon investigator evaluations.

5.2.5.1. Dose Modifications and Delays

The following guidelines should be applied:

Following resolution of toxicity to baseline or \leq Grade 1, treatment is resumed at either the same or lower dose of study drug as per the criteria in [Table 2](#). If treatment is resumed at the same dose of study drug, and the same toxicity recurs with the same or worse severity regardless of duration, dose must be reduced to the next lower dose level. If treatment is resumed at the lower dose of study drug, and the same toxicity recurs with the same or worse severity, the subject should have a second dose reduction.

Subjects who are withdrawn from the study for a study related AE or an abnormal laboratory value must be followed as described in Section [5.2.5.2](#).

Table 1: Dose Reduction Scheme for Infigratinib

Dose Reduction	Starting dose level 0	Dose level -1	Dose level -2
-----------------------	-----------------------	---------------	---------------

Infigratinib	125 mg	100 mg	75 mg
--------------	--------	--------	-------

Table 2: Criteria for Interruption and Re-initiation of Infigratinib for AEs Considered to be Possibly Related to Infigratinib

Worst Toxicity CTCAE (v5.0) Grade (Unless Otherwise Specified)	Recommended Dose Modifications any Time During a Cycle of Therapy
CARDIAC DISORDERS	
Cardiac - Prolonged QTcF Interval	
Grade 1 and 2: QTcF \geq 481 msec and \leq 500 msec (asymptomatic)	
Monitor dose level of infigratinib. Two additional ECGs separated by at least 5 minutes should be performed to confirm the finding. If the finding is confirmed, single ECG assessments should be performed for 2 additional cycles at the same frequency as in Cycle 1, or as clinically indicated. If abnormality is detected, 2 additional ECGs separated by at least 5 minutes should be performed to confirm the finding.
 
 • If ECG assessments show no QTcF \geq 481 msec, for subsequent cycles ECG monitoring will be performed as per visit schedule. • If ECG assessments are still abnormal (QTcF \geq 481 msec and \leq 500 msec), then ECG monitoring must continue at the same frequency as in cycle 1 for all subsequent cycles.
Grade 3: QTcF > 500 msec as identified on the ECG by the investigator	
Hold infigratinib. Two additional ECGs separated by at least 5 minutes should be performed to confirm the finding. If the finding is confirmed, monitor subject with hourly ECGs until the QTcF has returned to baseline and perform further monitoring as clinically indicated.
 
 • Exclude other causes of QTcF prolongation such as hypokalemia, hypomagnesaemia and decreased blood oxygenation. • Subjects should receive appropriate electrolyte replacement and should not receive further infigratinib until electrolytes are documented to be within normal limits.
Grade 4: QTcF > 500 or > 60 msec change from baseline and Torsade de pointes or	
Once the QTcF prolongation has resolved, subjects may be retreated at one lower dose level at the investigator's discretion. Single ECG assessments should be performed for 2 additional cycles at the same frequency as in Cycle 1 or as clinically indicated. If abnormality is detected, 2 additional ECGs separated by at least 5 minutes should be performed to confirm the finding.
 
 ○ If ECG assessments show no QTcF \geq 481 msec, ECG monitoring will be performed as per visit schedule for subsequent cycles. ○ If ECG assessments are still abnormal (QTcF \geq 481 msec and \leq 500 msec), then ECG monitoring must continue at the same frequency as in cycle 1 or as clinically indicated, for all subsequent cycles. • Subjects who experience recurrent QTcF \geq 500 msec after one dose reduction will be withdrawn from study.
	Discontinue infigratinib.

Worst Toxicity CTCAE (v5.0) Grade (Unless Otherwise Specified)	Recommended Dose Modifications any Time During a Cycle of Therapy
polymorphic ventricular tachycardia or signs/symptoms of serious arrhythmia	If QTcF > 500 msec or > 60 msec change from the baseline is observed, a plasma sample for determination of infigratinib concentration should be obtained with the time of sample collection noted.
Cardiac Disorders – Others	
Gra de \geq 3, or congestive heart failure	Discontinue subject from study drug.
Gra de \geq 2	
INVESTIGATIONS-HEMATOLOGY	
ANC Decreased (Neutropenia)	
Gra de 3 (ANC < $1.0 - 0.5 \times 10^9/L$)	
Hold dose of infigratinib until resolved to CTCAE Grade \leq 1 or baseline, then
 
 • If resolved within \leq 7 days, maintain dose level of infigratinib • If resolved between > 7 days and 14 days, \downarrow 1 dose level of infigratinib • If not resolved within \leq 14 days, discontinue subject from study drug
Gra de 4 (ANC < $0.5 \times 10^9/L$)	
Hold dose of infigratinib until resolved to CTCAE \leq Gra de 1, \downarrow 1 dose level of infigra tinib
 
 • If not resolved within \leq 14 days, discontinue subject from study drug
Febrile Neutropenia	
Gra de 3 (ANC < $1.0 \times 10^9/L$, single temperature of > $38.3^{\circ}C$ or a sustained temperature of $\geq 38.0^{\circ}C$)	
Hold dose of infigratinib until resolved to CTCAE Grade \leq 1, then
 
 • If resolved within \leq 7 days, \downarrow 1 dose level of infigratinib. • If not resolved within 7 days, discontinue subject from study drug
Gra de 4	Discontinue subject from study drug
Anemia	
Gra de 3 (hemoglobin < 8.0 g/dL)	Hold dose of infigratinib until resolved or corrected to CTCAE Grade \leq 1 or baseline, then maintain dose level
Gra de 4	Hold dose of infigratinib until resolved or corrected to CTCAE Grade \leq 1 or baseline, then \downarrow 1 dose level
Platelet Count Decreased (Thrombocytopenia)	
Grade 3 (platelet < $50 - 25 \times 10^9/L$) without \geq Gra de 2 bleeding	
Hold dose of infigratinib until resolved to CTCAE Grade \leq 1 or baseline
 
 • If resolved within \leq 7 days, maintain dose level of infigratinib • If resolved between > 7 days and 14 days, \downarrow 1 dose level of infigratinib • If not resolved within \leq 14 days, discontinue subject from study drug
Grade 3 (platelet < $50 - 25 \times 10^9/L$) with bleeding or Grade 4 (platelet < $25 \times 10^9/L$)	
Hold dose of infigratinib until resolved to CTCAE Grade \leq 1 or baseline, then \downarrow 1 dose level
 
 • If not resolved within \leq 14 days, discontinue subject from study drug

Worst Toxicity CTCAE (v5.0) Grade (Unless Otherwise Specified)	Recommended Dose Modifications any Time During a Cycle of Therapy
INVESTIGATIONS – RENAL	
Serum Creatinine	
Gra de ≥ 2	If serum creatinine CTCAE Grade ≥ 2 has been demonstrated in conjunction with hyperphosphatemia, serum creatinine levels must be repeated at least weekly until resolution. 24-hour urine collection should be obtained as clinically indicated for total phosphate, calcium, protein, and creatinine clearance. Ultrasound examination of the kidneys should be performed as indicated to evaluate de-novo calcifications until resolution or stabilization of creatinine.
Gra de 2 ($\geq 2.00 - 3.0 \times \text{ULN}$ or $2.0 - 3.0 \times \text{baseline}$)	
Hold dose of infigratinib until resolved to Gra de ≤ 1 or baseline
 
 • If resolved within ≤ 7 days, maintain dose level of infigratinib • If resolved between > 7 days and 14 days, $\downarrow 1$ dose level of infigratinib • If not resolved within ≤ 14 days, discontinue subject from study drug
Gra de ≥ 3 ($> 3.0 \times \text{ULN}$ or $> 3 \times \text{baseline}$)	Discontinue subject from study drug
INVESTIGATIONS – HEPATIC	
AST or ALT	
Grade 3 ($> 5.0 - 20.0 \times \text{ULN}$) without bilirubin elevation $> 2.0 \times \text{ULN}$	
Hold dose of infigratinib until resolved to CTCAE Grade ≤ 1 or baseline
 
 • If resolved within ≤ 7 days $\downarrow 1$ dose level of infigratinib • If not resolved within ≤ 7 days, discontinue subject from study drug
Grade 4 ($> 20.0 \times \text{ULN}$) without bilirubin elevation $> 2.0 \times \text{ULN}$	Discontinue subject from study drug
AST or ALT and Bilirubin	
AST or ALT $> 3.0 - 5.0 \times \text{ULN}$ and total bilirubin $> 2.0 \times \text{ULN}$ without liver metastasis or evidence of disease progression in the liver	
Hold dose of infigratinib until both transaminases and bilirubin resolved to CTCAE Grade ≤ 1 or baseline.
 
 • If resolved within ≤ 7 days, $\downarrow 1$ dose level of infigratinib. • If not resolved within ≤ 7 days, discontinue subject from study drug
AST or ALT $> 5.0 \times \text{ULN}$ and total bilirubin $> 2.0 \times \text{ULN}$	Discontinue subject from study drug
LABORATORY / METABOLIC DISORDERS	
Asymptomatic Amylase and/or Lipase Elevation	
General Comment:	A CT scan or other imaging study to assess the pancreas, liver, and gallbladder should be performed as clinically indicated within 1 week of the first occurrence of any CTCAE \geq Grade 3 amylase and/or lipase
Gra de 3 ($> 2.0 - 5.0 \times \text{ULN}$)	
 • Hold dose of infigratinib until resolved to CTCAE Grade ≤ 2 • $\downarrow 1$ dose level of infigratinib

Worst Toxicity CTCAE (v5.0) Grade (Unless Otherwise Specified)	Recommended Dose Modifications any Time During a Cycle of Therapy
Gra de 4 ($> 5.0 \times \text{ULN}$)	
 • If not resolved within ≤ 14 days, discontinue subject from study drug 
For recurrent Grade 3 a symptomatic lipase or a mylase elevation despite dose reduction, drug should be held and continuation of therapy should be discussed with the medical monitor following resolution to \leq Grade 2.
 
For any Grade 4 a symptomatic lipase or a mylase elevation, drug should be held and continuation of therapy should be discussed with the medical monitor following resolution to \leq Grade 2.

Hyperphosphatemia	

Serum phosphorus $> 5.5 - 7.0 \text{ mg/dL}$
 
Serum phosphorus $> 7.0 \text{ mg/dL}$ for more than 7 days despite maximal phosphate-lowering therapy
 
Or, single serum phosphorus $> 9.0 \text{ mg/dL}$ regardless of duration or dose of phosphate lowering therapy
 
(Optimize/maximize dose and schedule of phosphate lowering therapy in accordance with package insert, country or institutional guidelines)
	
Maintain dose level of infigritinib and optimize phosphate lowering therapy as clinically indicated
 
 • Hold infigritinib dose until resolved to serum phosphorus $\leq 5.5 \text{ mg/dL}$. • Restart infigritinib at the same dose level with maximal phosphate binder dosing if the subject did not receive maximal phosphate binder dosing for serum phosphorus $> 7.0 \text{ mg/dL}$ for > 7 days. • Reduce one dose level of infigritinib if the subject had received maximal phosphate lowering therapy for serum phosphorus $> 7.0 \text{ mg/dL}$ for > 7 days or if subject had a one-time serum phosphorus of $> 9.0 \text{ mg/dL}$. Restart infigritinib with maximal phosphate binder dosing. 
It is recommended that phosphate binder dosing continues during infigritinib dose interruptions for hyperphosphatemia and that serum phosphorus values be monitored frequently, e.g., every 2-3 days.
 
Phosphate binder dosing should be held during the week off infigritinib therapy each cycle (Days 22-28) unless serum phosphorus is not normalized and during infigritinib dose interruptions for non-hyperphosphatemia AEs.

Hypercalcemia	
Serum calcium Gra de 2	
Hold infigritinib dose until resolved to Gra de 1 or baseline:
 
 • If resolved within ≤ 7 days after suspending infigritinib, maintain dose level • If resolved between > 7 days and 14 days after suspending infigritinib, $\downarrow 1$ dose level • If not resolved within ≤ 14 days, discontinue subject from study drug
Serum calcium \geq Gra de 3	Discontinue subject from study drug
NERVOUS SYSTEM DISORDERS	
Any Gra de 2 neurotoxicity	
Omit dose of infigritinib until resolved to CTCAE Grade ≤ 1, then $\downarrow 1$ dose level of infigritinib
 
 • If not resolved within ≤ 14 days, discontinue subject from study drug
Any Gra de ≥ 3 neurotoxicity	Discontinue subject from study drug

Worst Toxicity CTCAE (v5.0) Grade (Unless Otherwise Specified)	Recommended Dose Modifications any Time During a Cycle of Therapy
GASTROINTESTINAL SYSTEM DISORDERS	
Pancreatitis	
Gra de \geq 2	Discontinue subject from study drug
Diarrhea	
General Comment:	Antidiarrheal medication is recommended at the first sign of abdominal cramping, loose stools or overt diarrhea
Gra de 1	Maintain dose level of infiratinib, initiate anti-diarrheal treatment
Gra de 2	
 Hold dose of infiratinib until resolved to CTCAE Grade \leq 1 Optimize anti-diarrheal treatment For reoccurrence of diarrhea CTCAE Grade 2, hold dose of infiratinib until resolved to CTCAE Grade \leq 1, \downarrow infiratinib by 1 dose level
Gra de 3	
 Hold dose of infiratinib until resolved to CTCAE Grade \leq 1 Optimize anti-diarrheal treatment \downarrow infiratinib by 1 dose level For reoccurrence of diarrhea CTCAE Grade 3, despite optimal antidiarrheal treatment, discontinue subject from study drug
Gra de 4	Discontinue subject from study drug
Vomiting	
Gra de 2 not controlled by optimal anti-emetic therapy	Hold infiratinib doses until \leq Gra de 1, \downarrow 1 dose level 
 If not resolved within \leq 14 days, discontinue subject from study drug
Grade 3 not controlled by optimal anti-emetic therapy or Grade 4	Discontinue subject from study drug
EYE DISORDERS (CONFIRMED BY OPHTHALMOLOGIC EXAMINATION)	
Retinal Disorders	
Grade 2 central serous retinopathy and central serous retinopathy-like events	Hold infiratinib until resolved to \leq Grade 1 and continue ophthalmologic evaluation 
 If resolved within \leq 14 days, \downarrow infiratinib by 1 dose level If resolved after $>$ 14 days, discontinue infiratinib
Gra de 3 central serous retinopathy and central serous retinopathy-like events and any other Grade 3 eye disorders	Hold infiratinib until resolved to Gra de \leq 1 
 If resolved within \leq 14 days, \downarrow infiratinib by 1 dose level If resolved after $>$ 14 days, discontinue infiratinib
Grade \geq 1 retinal vein occlusion, Grade 4 central serous retinopathy and central serous retinopathy-like events, and Grade 4 other eye disorders	Discontinue subject from study drug
Other Ocular/Visual Toxicity	

Worst Toxicity CTCAE (v5.0) Grade (Unless Otherwise Specified)	Recommended Dose Modifications any Time During a Cycle of Therapy
Gra de \geq 3	
Hold infigra tinib until resolution to \leq Gra de 1
 
 • If resolution within \leq 14 days, \downarrow 1 dose level • If resolved after $>$ 14 days, discontinue infigritinib
GENERAL DISORDERS	
Fatigue	
Gra de \geq 3	
Hold dose of infigritinib until resolved to CTCAE Grade \leq 1
 
 • If resolved within \leq 7 days, maintain dose level of infigritinib. • If resolved after $>$ 7 days, discontinue subject from study drug
SKIN AND SUBCUTANEOUS TISSUE DISORDERS	
Alopecia	
Gra de 1	
Continue infigritinib
 
 • Minoxidil 5% (OTC) solution or foam once daily to scalp
Gra de 2	
Continue infigritinib
 
 • Minoxidil 5% (OTC) solution or foam twice daily to scalp • Fluocinonide 0.05% solution daily to scalp
Palmar-plantar erythrodysesthesia syndrome	
Gra de 0/1	
Continue infigritinib
 
 • Urea 20% or ammonium lactate 12% lotions bid to hands and feet
Gra de 2	
Continue infigritinib
 
 • Urea 20% or ammonium lactate 12% bid to hands and feet • Fluocinonide 0.05% cream bid to hands and feet
Gra de 3	
Hold infigra tinib until resolved to Gra de \leq 1
 
 • Urea 20% or ammonium lactate 12% bid to hands and feet • Fluocinonide 0.05% cream bid to hands and feet
Paronychia	
Gra de 1	
Continue infigritinib
 
 • Clindamycin 1% solution around and under nails tid • Soak for 15 minutes daily in white vinegar in tap water 1:1
Gra de 2	
Continue infigritinib
 
 • Cefadroxil 500mg bid or TMP/SMX DS bid for 14 days • Soak for 15 minutes daily in white vinegar in tap water 1:1 • Obtain bacterial cultures to confirm sensitivity to antimicrobial • Dermatology consultation

Worst Toxicity CTCAE (v5.0) Grade (Unless Otherwise Specified)	Recommended Dose Modifications any Time During a Cycle of Therapy
Gra de 3	
Hold infigra tinib until resolved to Gra de ≤ 1
 
 • Cefadroxil 500mg bid or TMP/SMX DS bid for 14 days • Obtain bacterial cultures to confirm sensitivity to antimicrobial • Dermatology consultation
Stomatitis	
Gra de 1	
Continue infigritinib
 
 • Dexamethasone elixir 0.5mg/mL swish and spit 1 teaspoon (5mL) tid.
Gra de 2	
Continue infigritinib
 
 • Dexamethasone elixir 0.5mg/mL swish and spit 1 teaspoon (5mL) tid.
Gra de 3	
Hold infigra tinib until resolved to Gra de ≤ 1
 
 • Dexamethasone elixir 0.5 mg/mL swish and spit 1 teaspoon (5 mL0 tid • Clotrimazole 10 mg lozenges qid
OTHER CLINICALLY SIGNIFICANT AEs	
Gra de 3	
Hold dose of infigritinib until resolved to CTCAE Grade ≤ 1, then \downarrow 1 dose level of infigra tinib
 
 • If not resolved within ≤ 14 days, discontinue subject from study drug
Gra de 4	Discontinue subject from study drug

Abbreviations: AE, adverse event; ALT, alanine aminotransferase; ANC, absolute neutrophil count; AST, aspartate aminotransferase; CT, computed tomography; CTCAE, Common Terminology Criteria for Adverse Events; ECG, electrocardiogram; QTcF, QTc corrected by Fridericia's formula; ULN, upper limit of normal.

